#### **1.e One-month phone follow-up**

Both treatment and control group will receive a follow-up phone call one month after the last session. The objectives of this phone call is to check if participants have any questions or problems of the program.

#### **1.f Safety and Adverse Events**

To avoid or minimize adverse events, we will ask participants to notify the rater or interventionist if they experience any discomfort (see 2.e risks and benefits). Testing and interviews will be terminated if participants develop fatigue, agitation, or emotional distress. Participants will be trained in exercise principles and recognize environment barriers and situations that is not safe to conduct the activities at the first visit.

#### **1.g Safety and Compliance Monitoring**

[name] will be responsible for reviewing study progress and outcomes including recruitment, data quality, safety and efficacy with the supervision of [name].

Because risk in the proposed study is considered minimal, the data monitoring plan will include continuous, close monitoring by the study investigator with prompt reporting of any adverse events. Given the small number of subjects undergoing treatment, problems will become more readily apparent through close monitoring of individual participants. In this study, [name] will monitor the study for adverse advents and adherence to the protocol and safety.

#### **1.h Definitions of Adverse Events**

Adverse events are defined as any unfavorable and unintended diagnosis, symptom, sign (including an abnormal laboratory finding), syndrome or disease which either occurs during the study, having been absent at baseline, or if present at baseline, appears to worsen. Adverse events are to be recorded regardless of their relationship to the study intervention.

Serious adverse event (SAE). An SAE is generally defined as any untoward medical occurrence that results in death, is life threatening, requires inpatient hospitalization or prolongation of existing hospitalization, results in persistent or significant disability/incapacity, is a congenital anomaly or is another condition which investigators judge to represent significant hazards

---

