## **C Study Objectives**

### ***C1 Primary Aim***

The primary aim of this study is to establish feasibility of Adapted LiFE and a RCT design.

WE hypothesis that the feasibility pilot study will have high reach (60% recruitment and 80% retention rate of targeted participants), acceptance (80% of participants rating high satisfaction with Adapted LiFE), adherence (80% of all exercise activities achieved during the intervention period for each participant), fidelity (90% consistency of elements delivered by occupational therapists throughout the study period), safety (no adverse events caused by Adapted LiFE), and appropriate efficacy measurement selection (70% of the participants do not show floor/ceiling effects among balance, muscle strength, and habit outcomes at pre- and/or post-tests).

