### **E2 Subject Selection and Withdrawal**

#### **2.a Inclusion Criteria**

Medically underserved older adults will be recruited by convenience sampling. Referrals from OT staff and members of a community advisory board of the Participation,

---

Environment & Performance Laboratory (PEPL) will be the main channels for recruiting medically underserved older adults. Inclusion criteria include:

- (1) age 70 or older;
- (2) live independently;
- (3) live in a medically underserved/health professional shortage area;
- (4) self-report two falls or one injurious fall in the past 12 months. The definition of a fall and injurious fall are described in Table 4.

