## **2.e Risks and Benefits**

### *Minimization of Risks and Confidentiality*

We are a HIPPA covered entity and comply with all HIPPA regulations. To protect against and minimize potential risks, participants will be carefully screened and evaluated for eligibility by research coordinator. Participants may have the risks of feeling tired or disrupted by home visits, sore muscles after practicing exercise activities, feeling worn out, or confidential information of participants may be accidentally disclosed. Participants may take a break at any time during participation and will be instructed to notify the rater or interventionist if they experience any discomfort.

An ID number will be assigned to each participant. All data collected from a participant will be labeled with the ID number. All participant electronic and hard-copy data will be kept under double-lock protection. All hard copy forms that contain personal identifiers (e.g., name, address, phone numbers) will be stored in a separate locked file drawer under double-lock protection. No publication or presentation of the study data will uniquely identify or provide sufficient information to uniquely identify participants.

To guard against unauthorized data access, all shared-use computer systems at the Washington University School of Medicine are protected with passwords, which are changed at 4-month intervals. Only individuals with a particular "need to know" status are given access, and system privileges are carefully restricted. All personal computers to be used in the Administrative Unit are located within a secure area, and the system is locked when not in use. SAS and SPSS software packages will be used for data management and analysis. Datasets generated from these programs will be password protected, which will make accessing study data difficult even in the event of unauthorized computer access occurs.

There is no proven benefit from being in this study. However, benefits to the participants enrolled in the proposed study are free in-home exercise sessions provide by OT interventionists. Participants in treatment group (Adapted LiFE) may be able to improve balance and muscle strength, and participants in the control group may be able to improve flexibility.

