## ***F2 Study Outcome Measurements***

Feasibility outcomes include reach, acceptance, adherence, fidelity, safety, and appropriate efficacy outcome selection are described below. Feasibility outcomes will be assessed by the visit-by-visit grid, rater/interventionist log, the LiFE activity planner, and the feasibility questionnaire.

Reach is defined by recruitment and retention rate. Recruitment rate will be measured by the percentage of residents successfully enrolled in the study. Retention rate will be defined by the percentage of enrolled participants who complete the program. Reach will be documented by OT interventionists in interventionist logs and visit-by-visit grids in REDCap.

Acceptance will be surveyed by the feasibility questionnaire at the last session. The questionnaire contains a question, “Are you satisfied with the Adapted LiFE program?,” using a seven-point Likert scale from one (very unsatisfied) to seven (very satisfied). Follow-up questions will be asked to explore what makes the program satisfying or unsatisfying to the participant.

Adherence will be defined as the average percentage of exercise activities achieved during the intervention period that are recorded in the Adapted LiFE activity planner.

Fidelity will be assessed as the delivery of active and essential ingredients of the program as recorded by OT interventionists in visit-by-visit grids in REDCap. OT interventionists will meet weekly with the principle investigator to review the delivery of essential and active ingredients of Adapted LiFE for quality assurance.

Safety of the program will be evaluated by the number of adverse events documented throughout the study duration. This will be documented by OT interventionists in interventionist logs and visit-by-visit grids in REDCap.

---

The visit-by-visit grid is a checklist of all the elements that the interventionist should cover during each session. The interventionist will fill out the grid after every session is completed.

The rater/interventionist log is a survey that each rater/interventionist need to fill out after each visit to document any adverse event or special notes from a participant.

The LiFE activity planner is a weekly calendar for participants to fill out during the intervention sessions. Participants will record and check off the activities that they have completed.

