**Table 2. Adapted LiFE intervention for medically underserved older adults**  
*Intervention composition*

Dosage and timing	Seven 40-60 minute sessions over 12 weeks (5 weekly session and 2 booster sessions). One follow-up phone call 1 month after the last session
Essential ingredients	
 
Iterative practice of goal setting and achieving outcome expectations to increase self-efficacy
 
Behavior change elicited by habit formation strategies
 

Active ingredients	
 
Exercise principles to increase balance and muscle strength
 
Cognitive capacity to remember and carry out planned activities
 

Approach	
 
Goal setting of exercise activities begins at low frequency
 
OT as a collaborative partner
 

Standardized elements of tailored approach	
 
Seven sessions to add 1-2 exercise activities to participant's routine
 
In-home training, active practice
 

*Note.* OT = occupational therapist.

Table 3. Adapted LiFE balance and strength training principles and activities

Balance Principles	Balance Activity
Decreasing base of support	Tandem stand Tandem walk One-leg stand
Shifting weight and moving to the limits of stability	Leaning side to side Leaning forwards and back wards
Stepping over objects	Stepping forwards and backwards Stepping side to side
Strength Principles	Strength Activity
Bend your knees	Bend knees
Sit to stand	Normal chair Low chair
On your toes	Stand on toes Walk on toes
On your heels	Stand on heels Walk on heels
Up the stairs	Up the stairs
Move sideways	Step sideways
Tighten muscles	Move ankles Bend / Straighten knees Tighten / Relax buttocks

---

Table 4. Definitions of a fall and injurious fall as inclusion criteria

Construct	Definition
Fall	A fall is an unexpected event in which a person comes to rest on the ground, floor, or a lower level
Injurious fall	An injurious fall is a fall with a physical injury, which can be categorized as minor, moderate, or serious injury
minor	Had minor bruises or abrasions not requiring health professional assistance and that caused reduction in physical function (e.g. due to pain, fear of falling)

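### The adverse event definition does not clearly cover a fall without injury, and the protocol body describes no fall question after screening, so the safety criterion could read as met with such falls uncounted

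*Combined protocol and SAP*

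**What the plan says.** C1 lists the safety criterion among the feasibility hypotheses: "safety (no adverse events caused by Adapted LiFE"). F2 gives its measure: "Safety of the program will be evaluated by the number of adverse events documented throughout the study duration".

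F 1.h defines an adverse event as "any unfavorable and unintended diagnosis, symptom, sign (including an abnormal laboratory finding), syndrome or disease". A further clause on timing restricts this to one "which either occurs during the study, having been absent at baseline, or if present at baseline, appears to worsen". It adds that events are recorded whatever their relationship to the intervention. Falls are not named in 1.h.

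To enter, a participant must "self-report two falls or one injurious fall in the past 12 months" (E2 2.a). Table 4 in K1 describes a fall as an unexpected event that leaves a person on the ground, floor or a lower level, and grades injury as minor, moderate or serious. Its title confines it to eligibility: "Definitions of a fall and injurious fall as inclusion criteria".

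The screening interview asks how many falls occurred in the past year (F 1.a). In the safety section, "we will ask participants to notify the rater or interventionist if they experience any discomfort" (F 1.f). The risk list in E2 2.e begins "Participants may have the risks of feeling tired or disrupted by home visits" and goes on to sore muscles, feeling worn out and accidental disclosure of information. It does not mention falling.

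**The concern.** The programme teaches tandem stands, tandem walking and one-leg stands at home (Table 3) to people who have all fallen recently. In the early stages they check with the interventionist before making an activity harder. By the end of session 7 they are expected to perform and upgrade activities on their own (F 1.c). A fall during practice is the most obvious harm to look for.

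The safety criterion is a zero count, so it depends wholly on what is eligible to be counted and on whether anyone asks. If one kind of fall is outside the definition, or is never elicited, a zero can reflect ascertainment and not safety. The pilot is also meant to test the protocol of the future trial, using the same design (E1), so a gap in recording falls would carry forward.

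**Working it through.** The plan states no fall rate and no adverse event rate, so there is no figure to reproduce. The check is mainly textual.

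**Step 1: is the event eligible?** Take a participant who loses balance in a one-leg stand, ends up on the floor and is unhurt.
- Under Table 4 this is a fall. Table 4 is invoked only for inclusion.
- Under 1.h it must be a diagnosis, symptom, sign, syndrome or disease. An event with no injury and no symptom is not plainly any of these.
- The baseline clause does not settle the matter. Everyone enters with a fall history, and 1.h does not say whether a further fall is new.

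Now take the same fall with a bruise, pain or a fracture. That is a sign, symptom or diagnosis and meets 1.h. If it leads to inpatient admission it meets the serious adverse event definition.

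**Step 2: is it elicited?** The contacts described in the protocol body are:
- Screening (F 1.a): asks about falls in the past year. This precedes enrolment and cannot feed the safety count.
- Sessions 2 to 5, both arms (F 1.c): a check for problems.
- Sessions 6 and 7, both arms (F 1.c): a check on progress and safety.
- Post-test T2 (F 1.b table, F 1.d, F2): balance, strength, habit and balance-confidence measures, with the feasibility questionnaire. No fall item is described.
- Phone call T3 (F 1.e): questions or problems with the programme.
- Rater/interventionist log (F 1.i, F2): adverse events and any special notes.

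Falls are named only at screening.

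**Step 3: where would it be recorded?** If the participant mentions the unhurt fall, the interventionist can log it as an adverse event or write it as a note. F2 counts adverse events; a note is not part of that count. Two interventionists could treat the same fall differently and both be following the text.

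**Step 4: size, for illustration only.**
- Inputs from the documents: 8 participants in the Adapted LiFE arm and 12 weeks of sessions (A1); reporting runs to the one-month call (F 1.k), taken here as 4 more weeks, so 16 in all; a 31% fall reduction cited for LiFE (A).
- Assumption: 1 to 2 falls per person-year, a range suggested by the entry rule and not a follow-up rate from the documents.
- Exposure: 8 × 16/52 = 2.46 person-years.
- Expected falls of any cause: 2.46 × 1 = 2.5 to 2.46 × 2 = 4.9.
- With the 31% reduction: × 0.69 gives 1.7 to 3.4.
- Chance of at least one fall in the arm, assuming a Poisson count: 1 − exp(−1.70) = 82% at the lowest of these, 1 − exp(−4.92) = 99% at the highest.

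Under these assumptions the question of how to classify a fall is likely to arise. The figures do not give the number of falls caused by the programme, the number without injury, or the number missed.

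**Step 5: what a zero would mean at best.** With complete capture, 0 of 8 participants has a one-sided 95% upper limit of 1 − 0.05^(1/8) = 31.2%. Incomplete capture makes a zero less informative still.

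**The case against.** The strongest reply is that collection is broader than 1.f suggests. The discomfort sentence there is about preventing adverse events. Collection runs through logs completed on the day of each visit or call (F 1.i), the problem and safety checks in both arms (F 1.c), the phone call (F 1.e) and close monitoring of individual participants (F 1.g). An attentive therapist would often hear of a fall. The log form and the appendices were not available, so a fall item on a form cannot be excluded.

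All of that stands, and it narrows the point. It does not close the gap, because no described check names falls and 1.h does not tell staff to count one that caused no injury.

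A reader might go further in four ways that the documents do not support:
- That falls in general escape the safety count. Falls with injury or symptoms meet 1.h if reported.
- That a further fall is excluded because falls were already present at baseline. A fall months earlier is history, and a later one can fairly be called new. The clause is unclear; it does not exclude.
- That participants are all repeat fallers who progress without supervision. One injurious fall is enough to enter, and upgrading is checked with the interventionist early on.
- That reporting is uneven between arms because only Adapted LiFE participants keep a planner. The planner records completed activities, not falls, and controls receive the same check for problems. Any imbalance is conjecture.

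**Conclusion.** The point holds for falls without injury or symptoms, and for falls that participants do not mention because nobody asks. For these, the plan followed as written can return no adverse events caused by Adapted LiFE when a fall did occur during a programme activity. Because this bears on a primary-aim criterion, it should be corrected.

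The conclusion rests on the protocol body and would weaken if the log form already carries a fall question. The number of falls affected is unknown. The range of 2.5 to 4.9 (1.7 to 3.4 with the cited reduction) covers falls of any cause at an assumed rate. A reader might take it as the number of missed events, or as the chance of failing the criterion; it is neither, since the criterion concerns only events caused by Adapted LiFE.

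**What to change.** - In F 1.h and F2, state that every fall after enrolment, by the Table 4 definition and with its injury grades, is recorded as a safety event regardless of injury or fall history. Record what the participant was doing at the time, since attribution to the programme depends on it.
- Add one fixed question to the rater/interventionist log, for example whether the participant has fallen since the last contact. Ask it at every session, at T2 and at T3, in identical words in both arms.
- Add falling to the risks listed in E2 2.e.
- Report falls by arm beside the adverse event count, identifying those that happened during a programme activity or a study test.

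The cost is some protocol wording and one log question at contacts that already take place. No visit or instrument is added. The downside is a safety tally that may look less favourable.

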### **1.i Data Collection Procedures for Adverse Events**

Adverse events will be recorded in rater/interventionist log within the same day of the visit or phone call. [name] and [name] will discuss if the participants need to be withdraw when an adverse event occur within 2 days.

Should there be a serious adverse event that occurs that increases the risks to the participants, the study will be stopped, an investigation will be conducted, and a findings report will be generated before the study is resumed(see 5.d).

Data of the withdrawn subjects other than reasons of withdrawal and demographic information will be deleted and excluded from data analysis.

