## **G4 Missing Outcome Data**

For feasibility outcomes, all data will be used in the final data analysis. Participants who have missing data will still be included.

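### F 1.i excludes withdrawn participants' data from analysis, which conflicts with G4 and with the F2 adverse-event count and can flatter the safety and adherence results

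*Combined protocol and SAP*

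**What the plan says.** The adverse-event data section, F 1.i, ends: "Data of the withdrawn subjects other than reasons of withdrawal and demographic information will be deleted and excluded from data analysis". Nothing in the document exempts adverse-event records, activity planners, visit grids or pre-test scores.

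Other sections point the other way or bear on the same data:

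- **G4** states: "For feasibility outcomes, all data will be used in the final data analysis". It adds: "Participants who have missing data will still be included".
- **F2, safety**: "Safety of the program will be evaluated by the number of adverse events documented throughout the study duration". The source is named too: "This will be documented by OT interventionists in interventionist logs and visit-by-visit grids in REDCap".
- **F2, adherence**: "Adherence will be defined as the average percentage of exercise activities achieved during the intervention period", read from the activity planner.
- **C1** sets the targets: "adherence (80% of all exercise activities achieved during the intervention period for each participant") and "safety (no adverse events caused by Adapted LiFE").
- **E2 2.g** holds a withdrawn participant's information in REDCap up to study completion.
- **E2 2.f and F 1.i** give the routes to withdrawal: the participant's own choice, a serious adverse event bearing on safety, and a staff discussion after an adverse event.
- **F 1.j** sends serious adverse events to the Human Research Protection Office (HRPO). **F 1.k** runs the reporting period from enrolment to the one-month call.

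**The concern.** Safety and adherence are primary-aim targets in C1, and B2 says the pilot's results will inform whether the main study should go ahead. Adverse events are one route to withdrawal, so a rule that removes withdrawn participants' records can fall selectively on people who had events. Those who leave may also be those who practised least. Followed as written, F 1.i would leave a safety count that is not the one F2 defines, and an adherence average taken over completers only. Staff also have conflicting instructions: G4 tells the analyst to use everything, while F 1.i tells the analyst to leave these participants out.

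**Working it through.** The plan has no figure of its own to reproduce: G1 sets 16 participants without a calculation. The check compares the texts, then asks when exclusion would change a C1 verdict.

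**1. The texts side by side.** For a withdrawn participant, F 1.i leaves only the withdrawal reason and demographics. F2 takes the safety count from interventionist logs and visit grids, which are not among the items kept. Withdrawal reasons are not listed as a source for the count. If a withdrawn participant had an event that was not the withdrawal reason, the F2 count cannot be produced as defined. 2.g leaves the timing of deletion unclear (keep until completion, then delete, is a possible reading), but F 1.i states exclusion from analysis either way.

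**2. Safety.** What drops out is mainly non-serious events that were not the reason for withdrawal, for example the muscle soreness that 2.e lists as a risk. Removing records can never raise a count. If the only intervention-caused event in the Adapted LiFE arm is one of these, the count goes from 1 (target missed) to 0 (target met).

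**3. Mean adherence, Adapted LiFE arm only** (3.b removes the self-monitoring calendar from the control arm). Inputs: 8 in the arm (A1); target 80% (C1); completers' mean c, assumed at 81.3% (the preliminary pilot's average, D1), 85% or 90%; w withdrawn, with mean adherence x.

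Mean with withdrawn participants kept = ((8 − w)c + w·x)/8. With them excluded, the mean is c, which meets 80% at all three levels. The verdict therefore changes when

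x < (8 × 80 − (8 − w)c)/w.

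| Completers' mean c | One withdrawn: 640 − 7c | Two withdrawn: (640 − 6c)/2 |
|---|---|---|
| 81.3% | 640 − 569.1 = 70.9% | (640 − 487.8)/2 = 76.1% |
| 85% | 640 − 595 = 45% | (640 − 510)/2 = 65% |
| 90% | 640 − 630 = 10% | (640 − 540)/2 = 50% |

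At or above these values the verdict stands. If withdrawn participants adhered as well as completers, there is no bias.

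**4. Floor/ceiling criterion (70%, C1).** Suppose it is judged as one yes/no per participant at pre-test (T1) in all 16. With 11 unaffected, 11/16 = 68.8% misses; excluding one affected participant gives 11/15 = 73.3%, which meets. The shift can also go the other way: 12/16 = 75.0% meets, and excluding three unaffected participants gives 9/13 = 69.2%, which misses. C1 does not say that the criterion is pooled in this way, and F2 defines this outcome by ease of administration instead, so these figures are illustrative only.

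**5. Would the clause come into play?** Counting every non-completer as withdrawn, and taking withdrawals as independent, the chance of at least one among 8 is 1 − 0.8^8 = 83.2% at the C1 retention target and 1 − (8/9)^8 = 61.0% at the preliminary pilot's reported 8 of 9. D1 gives both 11 and 9 as the number enrolled, so the second input is itself uncertain. These are chances that someone withdraws, not that a verdict changes.

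**The case against.** **G4 may be the general rule and F 1.i its exception.** G4 is headed as a missing-data section and does not mention withdrawn participants. That reading is possible, though G4 does not say so. It does not rescue the F2 safety count, which is meant to cover the whole study.

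**The clause may be narrower than it looks.** It sits in the adverse-event section and may cover only withdrawals prompted by adverse events. This ambiguity stands. The conflict exists under both readings, and under the narrow one the exclusion falls on exactly the people who had events. The triggering event would then survive as the retained reason, so a change in the safety verdict would need a further caused event in the same person and no other caused event in the arm.

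**Causality is not operationalised.** C1 counts events caused by Adapted LiFE, F2 counts all documented events, and no section says how cause is judged. The safety target is therefore unclear even with nothing removed. That stands.

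**The targets carry no formal decision rule.** G1 says the pilot does not test hypotheses, G2 summarises feasibility descriptively, and no progression rule is attached to C1. This limits the consequence but does not remove the bias in what is reported.

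A reader might also infer more than the documents support:

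- *That the data are irrecoverably lost before analysis.* 2.g may mean they still exist then; F 1.i gives no time of deletion.
- *That the safety record disappears.* Withdrawal reasons are kept and serious events go to the HRPO.
- *That retention is distorted.* It is not, provided withdrawn participants stay in the enrolled denominator.
- *That fidelity is inflated.* It is recorded session by session, and nothing suggests that sessions given to people who later withdraw were delivered less faithfully.

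**Conclusion.** The conflict between F 1.i and both G4 and F2 is real on the plain wording and should be fixed. The possible effect on safety has one direction: the analysed count can fall but not rise, and a single lost event is enough if it was the only caused one. The effect on mean adherence is conditional on withdrawn participants having adhered less than completers, and its size depends on assumed adherence levels. One withdrawal changes the verdict easily if completers average close to 80% and hardly at all if they average 90%. The floor/ceiling effect depends on a definition that the document does not settle.

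A reader might conclude that the pilot's feasibility verdicts will be wrong. The documents do not support that: they give no basis for estimating how often a verdict would change. Confidence is high for the textual conflict and much lower for any changed result. Whether the 80% adherence target is a mean (F2) or applies to each participant (C1) is a separate question; the figures here use the mean.

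**What to change.** Replace the final sentence of F 1.i with a statement that all adverse events and all data collected up to withdrawal are kept and analysed, unless the participant withdraws permission for their use. State that the safety outcome counts every documented adverse event, whether or not it led to withdrawal, and that adherence includes the planner data recorded by withdrawn Adapted LiFE participants. Bring 2.g, F2 and G4 into line with this.

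Before the text is settled, check what the consent form promises about data after withdrawal; it is not in the copy reviewed. The cost is a wording amendment with no new data collection. The downside is that some feasibility figures may be less favourable: an event may be counted that would otherwise have been left out, and adherence may come out lower.
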